4.0 ENROLLMENT PROCEDURES

4.1 Patient Enrollment

Patients will be approached for this study during the pre-transplant evaluation phase. Transplant physicians will evaluate the patient eligibility onto this study. Eligible patients willing to participate in the trial will sign an MCW IRB approved informed consent form. A Clinical Trials Office CRC will record the documentation of patient consent and proceed with registration procedures. All source documents that support eligibility including a signed informed consent/HIPAA and signed eligibility checklist, will be available, reviewed and eligibility verified. At the point of registration, a member of the study team will register the patient in the electronic database, including demographics, consent and on-study information. The patient will be assigned a unique sequence number for the study. The principal investigator (PI) of the study, [name], will be notified prior to enrollment. Pharmacy will be notified upon patient registration. If at any point in time a patient wishes to withdraw from the study, they may notify [name] verbally or in writing. There will be no further data collection for participants who elect to withdraw from the study.

Target enrollment is 40 (20 per group) and includes patients undergoing autologous HCT for MM at MCW. Half of the participants will be randomized via permuted block assignment with random block sizes to receive propranolol upon study entry. Informed consent will be obtained to access participants' full medical records to ascertain relevant demographic and medical data as outlined in Section 4.2. The patient must have signed informed consent prior to registration on the study. Due to the pilot and feasibility nature of this study, the need to monitor response to prophylactic beta-blocker usage in a medically ill population, as well as the objective nature of gene expression profiling, this pilot study will not be blinded. Patients will be enrolled before study commencement at Day -7. Total study duration will be up to 7 weeks for participants assigned to the intervention group (1 week pre-transplant through 6 weeks post-transplant) and 5 weeks for those in the control arm (1 week pre-transplant through 4 weeks post-transplant). Additional clinical information will be collected for 100 days post-transplant as identified in section 3.2.2.2.

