2.4 Treatment Plan

The study drug will be dispensed. Compliance will be monitored by the clinical research coordinator (CRC). Beta-blocker tolerability will be assessed clinically by the treating physician on a weekly basis and for 1 week following cessation of beta-blocker therapy; subjects will be questioned about specific side effects as well as assessed for blood pressure and heart rate during weekly appointments or by phone.

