2.4.2 Study interruption

Participants needing to stop beta-blocker therapy secondary to intolerance or new onset of a contraindication will not be considered for resumption of therapy. Outcome and medical data will continue to be collected and assessed for intervention arm participants despite an inability to remain on beta-blocker therapy for the study duration.

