2.4.3 Beta-blocker weaning

Beta-blocker will be weaned for one of three reasons: 1) completion of drug intervention (28 ± 2 days post-transplant), 2) intolerance secondary to side effects, or 3) onset of new medical symptoms rendering beta-blocker therapy as contraindicated (see section 2.3.2). For patients that are at 40 mg twice daily at the time of weaning, the dose will be reduced to 20 mg twice daily for one week before being discontinued entirely. For patients who are on 20 mg twice daily at the time of weaning, their dose will be stopped altogether.

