In some cases if the patient stops taking propranolol all of a sudden the patient may develop chest pain that is worse and in some cases a heart attack may occur. This risk may be greater if the patient has certain types of heart disease. To avoid side effects, do not stop taking propranolol all of a sudden, if the patient wants to slowly stop this drug as ordered by their doctor. The patient should call the doctor right away if the patient has new or worse chest pain or if other heart problems occur.

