4.7 Study Monitoring

The follow-up schedule for scheduled study visits is outlined in Table 4.7a with study assessment time points described in Table 4.7b.

TABLE 4.7a. FOLLOW-UP SCHEDULE

Study Assessment Time Point	Target Day
Baseline	Up to Day -7
Pre-Transplant	Day -2 ± 1 day ¹
Day 0	Date of transplant
1 week	7 ± 2 days
2 weeks	14 ± 2 days
3 weeks	21 ± 3 days
4 weeks ²	28 ± 3 days
5 weeks ³	35 ± 3 days
6 weeks ³	42 ± 3 days
Next clinic appointment	~8 weeks (post-transplant)
14 weeks	100 ± 2 weeks

¹Assessment must occur prior to any conditioning regimen

² Research samples only can be collected ± 7 days from target day

³Assessment time points for intervention arm only

TABLE 4.7b. PATIENT CLINICAL ASSESSMENTS

Study Assessments/ Testing	Baseline	Day									
		-2	0	7	14	21	28	35	42	Next clinic appt.	100
Demographics (patient-, disease-, and treatment-related)	X										
Additional descriptive outcomes				X	X	X	X				X
Socioeconomic status	X										
Hospital Anxiety and Depression Scale (HADS)	X		X	X	X	X					
Blood draw for gene expression analysis	X	X					X				
Pregnancy test for FCBP	X										
Toxicity			X	X	X	X	X	X ¹	X ¹		
Assessment of adherence ²		X					X			X	
Heart rate and blood pressure	X		X	X	X	X	X			X	
Myeloma response assessment											X

Consent has to occur within 30 days prior to starting study drug

Numbers indicate days relative to day of transplant, with day of transplant being 0

Patients will be enrolled and randomized prior to commencement of study drug/control arm

¹ For Propranolol group only. Patients will have toxicity assessed weekly and once more 7 days \pm 3 days after discontinuing drug.

²Adherence will be assessed weekly or monthly based on number of pills prescribed.

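### A propranolol participant who withdraws from the study leaves the recorded post-discontinuation safety check and Day 100 follow-up, and the plan does not ask what they are withdrawing from

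*Combined protocol and SAP*

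**What the plan says.** Section 4.1 allows a participant to leave at any time ("If at any point in time a patient wishes to withdraw from the study") by telling the study lead, and then states: "There will be no further data collection for participants who elect to withdraw from the study". The rule covers both arms and has no exception for safety follow-up.

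Other sections bear on the same participant:

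- **Section 2.4** has the treating physician assess propranolol tolerability "on a weekly basis and for 1 week following cessation of beta-blocker therapy".
- **Table 4.7b, footnote 1**, for the propranolol group: "Patients will have toxicity assessed weekly and once more 7 days" (± 3 days) after the drug is discontinued.
- **Section 2.4.2**, on stopping for intolerance or a new contraindication: "Outcome and medical data will continue to be collected and assessed for intervention arm participants despite an inability to remain on beta-blocker therapy".
- **Section 2.4.3**: "Beta-blocker will be weaned for one of three reasons". The three are planned completion, intolerance and a newly arising contraindication.
- **Section 2.6** tells participants "do not stop taking propranolol all of a sudden", because chest pain may worsen and a heart attack may occur. It repeats this as the boxed warning.
- **Sections 3.2.2.2 and 5.4.2.2** follow response, treatment-related mortality (TRM), progression-free survival (PFS) and overall survival (OS) to Day 100. For the three time-to-event outcomes, loss to follow-up ends observation.

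**The concern.** The plan names a serious risk tied to stopping propranolol and schedules an assessment about a week after stopping. For a propranolol participant who withdraws from the study, Section 4.1 switches off the recording of that assessment. The same participant has no stated weaning route, since Section 2.4.3 does not mention the participant's choice.

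Two things are at stake. The first is the safety record. Section 4.1 leaves the trial unblinded, and Section 3.2.2.1b accepts that side effects influence whether people stay on the drug. Some withdrawals on propranolol may therefore be related to toxicity, and the events missed would then not be a random subset. The Appendix B stopping rule turns on more than 2 of 10 participants having a life-threatening or fatal event, so a single unrecorded event could matter.

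The second is the Day 100 outcomes. Kaplan-Meier estimates, the log-rank test and Gray's test all take censoring at loss to follow-up as unrelated to prognosis. Withdrawal that depends on how the participant is doing would break that assumption.

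**Working it through.** The point rests on reading the sections together. The arithmetic only gives a sense of scale, and the plan states no figure of its own to reproduce.

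**Step 1. Which participants keep which data.**

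| Participant on propranolol | Check after stopping (2.4; Table 4.7b fn 1) | Continued outcome data | Weaning reason in 2.4.3 |
|---|---|---|---|
| Completes the course | Yes | Yes | Listed |
| Stops for intolerance or contraindication, stays in study | Yes | Yes, expressly (2.4.2) | Listed |
| Stops by choice, stays in study | Yes; the check is not limited by reason | Not excluded; 2.4.2 speaks only of inability | Not listed |
| Withdraws from the study | Required by 2.4 and 4.7, but not recorded under 4.1 | Ended by 4.1 | Not listed |

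Only the last row contains a direct conflict. The third row is a matter of silence.

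**Step 2. How many.** Section 5.2 enrols 40 and aims for 30 with complete gene data, with 15 in the intervention group.

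- Overall planned loss: (40 − 30)/40 = 25%.
- Intervention arm: (20 − 15)/20 = 25%, or 5 participants.

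These losses concern complete gene data and combine attrition with drug intolerance. Intolerant participants are still followed under Section 2.4.2. The 5 is therefore not an estimate of voluntary withdrawal. As an assumption, I take 0 to 5 of 20 (0–25%), with 5 as an extreme upper end.

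**Step 3. What the loss does to a zero-event statement.** If no post-stop cardiac event is seen among n participants followed, the one-sided 95% upper bound is 1 − 0.05^(1/n).

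| Withdrawn (assumed) | n followed | Upper bound |
|---|---|---|
| 0 | 20 | 1 − 0.05^(1/20) = 13.9% |
| 1 | 19 | 1 − 0.05^(1/19) = 14.6% |
| 2 | 18 | 1 − 0.05^(1/18) = 15.3% |
| 5 | 15 | 1 − 0.05^(1/15) = 18.1% |

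The loss of precision is small for one or two withdrawals, and 20 participants say little about a rare cardiac event in any case. The greater worry is selective loss, which this bound does not measure and the documents do not allow us to quantify.

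**The case against.** The strongest reply is that this is a drafting gap. Several parts of that reply stand.

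- **Stopping the drug is not leaving the study.** A reader might infer that anyone who gives up propranolol by choice loses the safety check. The documents do not support that. Section 4.1 applies to withdrawal from the study, and the checks in Section 2.4 and Table 4.7b are not limited by reason for stopping. A participant who stops by choice and stays in the study keeps them.
- **Section 2.4.2 is not exclusive.** It retains data for those unable to stay on the drug. It does not say that only they are retained.
- **Many side-effect stops are already covered.** Intolerance is a listed reason for weaning and its data are kept. The bias argument therefore concerns only those who leave the study altogether.
- **Data collection is not care.** Section 4.1 ends the research record. Nothing in it ends the treating physician's care or cancels the warning in Section 2.6. Section 4.3.3 and Appendix B require fatal and life-threatening events to be reported once the investigator is aware of them, and they state no exception for withdrawn participants. How that fits with Section 4.1 is unclear, but it would be too strong to say that the risk goes wholly unobserved.
- **Withdrawers may not be the ones who stop most abruptly.** That is inference with no source in the documents. Section 2.4.3 itself has some participants stop without a step-down, and they remain followed.
- **The consent form is not available here.** It may say more about withdrawal, and ending collection at a participant's request respects their choice.

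None of this removes the conflict in the protocol text for a propranolol participant who withdraws from the study.

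**Conclusion.** The point holds for participants on propranolol who withdraw from the study. Section 4.1 ends their data collection, while Section 2.4 and Table 4.7b, footnote 1, call for an assessment after discontinuation whatever the reason. Section 2.4.3 offers no weaning reason that fits them, despite the warning in Section 2.6. What is lost is the scheduled safety record and the Day 100 outcomes; clinical care is not shown to be lost.

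The number affected is not given, and 0 to 5 of 20 is my assumption. It would be tempting to read the 10 of 40 in Section 5.2 as the expected withdrawals, or to conclude that propranolol will look safer than it is. The first misreads a figure about gene data. The second claims a direction that nothing in the documents establishes. The supportable statement is that safety on propranolol may look better than it is, and that censoring for PFS, OS and TRM may be informative, if withdrawal is related to side effects or prognosis.

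**What to change.** In Section 4.1, when a participant asks to leave, ask and record whether they are (a) stopping study drug and procedures only, or (b) also declining further data collection. Do not presume (a) by default.

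If the participant agrees, keep the toxicity check already scheduled 7 ± 3 days after discontinuation and chart-based outcomes to Day 100. End all collection if they decline. First confirm that the consent covers this, because Section 4.1 ties record access to the variables in Section 4.2, which are baseline and treatment characteristics.

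Sections 2.4, 2.4.2, 2.4.3, 2.6, 4.1 and 4.7 must be reconciled on how drug stopping and follow-up are handled for a participant who withdraws. No clinical rule is proposed here.

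The cost is one paragraph in the protocol, a consent edit, and one extra question plus a phone or chart check for a few participants.

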4.2 Baseline Demographic-, Disease-, and Treatment-Related Variables

Patient-related:

- Age at transplant
- Gender
- Race: Caucasian vs. African American vs. Asian/Pacific Islander vs. Other
- Body Mass Index: <18.5 vs. 18.5-24.9 vs. 25-29.9 vs. >=30
- Smoking status in 3 months prior to HCT (Y/N)
 - Household income prior to disease diagnosis: <\$23,000, \$23,000-\$34,999, \$35,000-\$44,999, \$45,000-\$54,999, \$55,000-\$64,999, \$65,000-\$74,999, >\$75,000
- Number of individuals in patient's household
- Education level: < high school vs. high school graduate vs. some post high school education vs. college degree vs. professional degree

Disease-related:

- International Stage
- Disease status prior to transplant: complete response, very good partial response, partial response, or stable disease
- Cytogenetics: high risk vs. standard risk by International Myeloma Working Group (IMWG) criteria

Treatment-related:

- Number of CD34+ cells infused/kg of recipient body weight
- Transplant setting: inpatient vs. outpatient transplant (defined as patients who plan to stay outpatient during entire transplant period)

4.3 Data and Safety Monitoring Plan

4.3.1 Guideline for serious adverse event reporting

Please refer to Appendix B for more details on adverse event reporting.

4.3.2 Monitoring the progress of the trial and safety of participants

This randomized controlled pilot study will be monitored by the PI, [name]. The PI will review the outcome of the data for each individual patient on an ongoing basis. The PI will have primary responsibility for ensuring that the protocol is conducted as approved by the IRB. The PI will ensure that the monitoring plan is followed and that all data required for oversight of monitoring are accurately reported, that all AEs are reported according to the protocol guidelines, and that any AEs reflecting patient safety concerns are appropriately reported.

4.3.3 Adverse event reporting

The capture of toxicities and AEs in this protocol will follow the same approach and will be done in two levels. First, grades 3-5 AEs will be collected at different time points during the study period. Any AE that fulfill this criterion will be captured and the frequency of each organ toxicity tabulated. The Data and Safety Monitoring Committee (DSMC) and IRB will receive a summary of all the AEs captured in calendar forms in a quarterly to biennial basis depending the schedule of protocol review meetings. Additionally the PIs will review the frequency of toxicities in a quarterly basis.

Second, any AE that is unexpected and of grades 3 to 5 will require expedited report to the oversight committees (MCW IRB, MCW DSMC and FDA – if applicable for studies under IND). The collection grades 3-5 unexpected AEs is event driven and requires a more comprehensive description of the event. The report for these AEs are termed Individual Case Safety Reports (ICSR) and include the following components: 1) summary cover sheet of the event, 2) narrative of the event, 3) associated conditions, medications and diagnostic information, source documents with further explanation of the event, and an evaluation of the event by the PI. The PI will review all these events and will determine if they require expedited reporting. If they are considered grades 3-5 and unexpected the report will be sent to the oversight committees within three days from acknowledgement of the event. If the event is not considered to fulfill criteria of grades 3-5 unexpected AE, it will be included in the DSMC and IRB reports for scheduled protocol reviews and will not require expedited reporting.

Reporting timelines:

1. **Fatal (grade 5) or Life Threatening** events must be reported within 24 hours but not later than three calendar days of the investigator's observation or awareness of the event.
2. **All other events grades 3-4 unexpected** events (non-fatal/non life-threatening) must be reported within 3 to 5 calendar days of the investigator's observation or awareness of the event.

This study will be reviewed by the Medical College of Wisconsin Cancer Center Data Safety Monitoring Committee (MCW CC DSMC). A summary of the MCW CC DSMC activities are as follows:

- Review the clinical trials for data integrity and safety
- Review all adverse events requiring expedited reporting as defined per protocol
- Review all Data and Safety Monitoring (DSM) reports
- Submit a summary of any recommendations related to study conduct
- Terminate the study if deemed unsafe for patients

A copy of the MCW CC DSM Plan and membership roster will be maintained in the DSMC file and updated as membership changes. The committee will review reports from the study PI twice annually (or more frequently if needed) and provide recommendations on trial continuation, suspension or termination as necessary. Any available DSMC letters will be submitted to the IRB of record as required.

4.4 Specimen Collection

The Cancer Center Lab draw blood to be stored in PAXGene RNA tubes at three study time points as described in Table 4.7b. These time points include baseline (Day -7), Day -2 (immediately prior to transplant, central line placement, or administration of any conditioning regimen), and Day +28. Blood will be drawn at one of two locations: in the hospital (if participants are immediately post-transplant and/or still or re-hospitalized) or in the transplant clinic during their regular visits. The PAXGene RNA tubes do not require any additional processing of blood samples before being frozen and sent to UCLA. These PAXGene RNA tubes will be stored at -80C in the Neuroscience Research Center, which is a locked facility, until they are batched and shipped to University of California Los Angeles (UCLA) for gene expression analysis. Before being stored they will be assigned a dummy ID that will be the sole identifier of the samples. The linked identifiers will be stored on a secure computer network through the CIBMTR under the PI's name. Samples will be packaged with dry ice and shipped overnight to [name] lab at UCLA at the time of study conclusion. This will be done on a day such that the UCLA lab can receive and keep the samples frozen at -80C. Our groups have collaborated successfully on transfer of samples in the past. All samples will be sent together.

4.5 Gene Expression Profiling

The UCLA Social Genomics Core (Directed by [name], Consultant) will conduct all gene expression profiling on obtained blood samples by using Illumina HT-12 human gene expression bead arrays.⁴⁴ Total RNA will be extracted from the whole blood samples stored at MCW, subjected to quality assurance assays to test suitable mass (by spectroscopy) and integrity (by Agilent Bioanalyzer RNA Integrity Score) for analysis, and subjected to microarray target synthesis and hybridization in collaboration with the UCLA Neuroscience Genomics Core Laboratory using standard Illumina assay equipment and protocols. The output of these analyses is quantification of whole genome

RNA production, which will be analyzed as per the methods below (section 5.4.1). Patient-level genetic data from [name] lab will not be conveyed to the patient or the clinician and no clinical decision will be made on the basis of genetic findings.

4.6 Psychosocial Assessments

4.6.1 Socioeconomic status

SES will be assessed by household income prior to diagnosis with MM. This information will be collected from participants at baseline/time of study enrollment. The 2012 median family income in Wisconsin was \$51,059 (US median was \$51,371) according to the US American Community Survey (<http://www.census.gov/prod/2013pubs/acsbr12-02.pdf>) with the poverty threshold of \$23,050 for a four-person family. Thus, we categorized family income as <\$23,000, \$23,000-\$34,999, \$35,000-\$44,999, \$45,000-\$54,999, \$55,000-\$64,999, \$65,000-\$74,999, >\$75,000. Education level (< high school vs. high school graduate vs. some post high school education vs. college degree vs. professional degree) will also be collected but not used as the primary indicator of SES in analyses.

4.6.2 Anxiety and depression

Participants will complete a HADS for primary analysis with gene expression at three study time points as described in Table 4.7b. These time points include baseline (Day -21), Day -2 (immediately prior to conditioning regimen), and Day +28. Further, HADS will be administered/assessed weekly in coordination with weekly beta-blocker assessment to ascertain further whether the beta-blocker might be affecting depression or anxiety.

HADS is a 14-item scale that generates ordinal data and is specifically designed to avoid reliance on somatic symptoms that are concomitant with medical illness. Participants can score between 0 and 21 for either anxiety or depression. Each item is scored on a scale of 0-3. A cut-off point of 8 or above on HADS-A (7 items) and HADS-D (7 items) has been established to connote significant anxiety or depression, respectively.⁴² Anxiety and depression will be evaluated both continuously as well as categorically with a cutoff of 8 to signify an abnormal level of anxiety or depression. Participants scoring at this level will be offered a referral to the MCW Psycho-Oncology program for further evaluation and treatment.

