3.2 Secondary Endpoints

3.2.1 Gene expression

3.2.1.1 Gene expression based on psychosocial factors

Expression levels of beta-adrenergic mediated gene expression will be compared between individuals with high vs. low levels of depression and anxiety, defined as a score of 8 or above on the Hospital Anxiety and Depression Scale (HADS) anxiety (HADS-A, 7 items) and depression subscales (HADS-D, 7 items)⁴² at all three blood draw timepoints. Expression differences will be assessed both dependently and independently of treatment group assignment.

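### Table 4.7b omits HADS at Day -2 and Day 28, where section 4.6.2 requires it for pairing with gene expression; the stated baseline day also differs between HADS and blood.

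*Combined protocol and SAP*

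**What the plan says.** Section 4.6.2 sets the HADS schedule for the expression analysis and points to the table as its source: "Participants will complete a HADS for primary analysis with gene expression at three study time points as described in Table 4.7b". It then names the days: "These time points include baseline (Day -21), Day -2 (immediately prior to conditioning regimen), and Day +28". It adds a second, more frequent schedule: "HADS will be administered/assessed weekly in coordination with weekly beta-blocker assessment".

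Section 3.2.1.1 plans to compare beta-adrenergic gene expression between patients with high and low HADS scores (cut-off 8) "at all three blood draw timepoints". Section 4.4 gives the draw days: "These time points include baseline (Day -7), Day -2 (immediately prior to transplant, central line placement, or administration of any conditioning regimen), and Day +28".

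In Table 4.7b the row "Blood draw for gene expression analysis" is marked at Baseline, Day -2 and Day 28. The HADS row is marked at Baseline and Days 0, 7, 14 and 21; its Day -2 and Day 28 cells are empty.

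**The concern.** The text relies on the table for a schedule that the table does not contain. Two of the three days on which HADS must be matched to expression have no HADS mark, and they are the two samples taken after propranolol starts. A site that used the table as its visit checklist would collect no HADS at either visit.

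A missed self-report score cannot be recovered later, whereas the blood is frozen and analysed in a batch at the end. The analyses exposed are the high/low HADS comparison in section 3.2.1.1, the models of anxiety and depression against the CTRA profile in section 5.4.1, and the last point of the HADS trajectory in section 5.4.2.2.

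**Working it through.** **1. The plan's own figure.** Section 4.6.2 says there are three HADS points paired with expression, as shown in Table 4.7b. Reading the rows across the table's 11 columns:

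| Row of Table 4.7b | Columns marked |
|---|---|
| HADS | Baseline, 0, 7, 14, 21 |
| Blood draw | Baseline, -2, 28 |
| In both rows | Baseline |

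The table gives 1 paired point, not 3, so the figure is not reproduced. Day -2 and Day 28 are missing.

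**2. Is the table being misread?** The HADS row has 11 cells for 11 columns. The blood-draw row falls on the days given in section 4.4. The adherence row falls on Days -2 and 28, as section 3.2.2.1b states, plus the later return visit. A sideways shift of the marks would not help: the three named points plus weekly scores at Days 7, 14 and 21 make six (Baseline, -2, 7, 14, 21, 28), and the row has five marks.

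**3. How far away is the nearest tabulated score?** Windows are from Table 4.7a.

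- Day -2 draw: ±1 day, so Day -3 to Day -1, and before any conditioning. The nearest later HADS is Day 0. Gap: 0 − (−1) = 1 day to 0 − (−3) = 3 days; nominally 2. The windows never meet, and conditioning falls between the two.
- Day 28 draw: research samples are allowed ±7 days, so Day 21 to Day 35. The nearest HADS is Day 21 ±3, so Day 18 to Day 24. Nominal gap: 28 − 21 = 7 days. Largest gap: 35 − 18 = 17 days. Smallest: 0, if the sample is taken early, between Days 21 and 24.

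**4. Number of paired observations.** Section 5.2 aims for 30 patients with complete gene data. Under the table: 30 × 1 = 30 same-visit pairs. Under the text, or with the two marks added: 30 × 3 = 90.

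**5. Baseline day.** Section 4.6.2 gives Day -21 for HADS and section 4.4 gives Day -7 for blood: nominally 21 − 7 = 14 days apart. Table 4.7a lets baseline fall on any day until Day -7, which can accommodate both, and Table 4.7b puts both assessments in one Baseline column. The difference therefore lies between two passages of text; the table creates no gap.

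**The case against.** The strongest reply is that the scores are planned. Section 4.6.2 requires HADS at Day -2 and Day +28 in so many words, section 3.2.1.1 agrees, and only one table row dissents. The weekly rule could also reach Day 28, although not Day -2. That stands. A reader might infer from the table that two of the three analyses cannot be done. The documents do not support this: it happens only if sites follow the table over the text, and nothing in the protocol says which prevails.

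A reader might also add the 14-day baseline gap to the two missing visits. The two cannot be combined. The missing visits arise under the table, where baseline HADS and blood share a column; the 14 days arise under the text, where no visit is missing.

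A third tempting reading is that the primary endpoint is at risk, because section 4.6.2 speaks of a primary analysis and Day +28 is the primary time point. But section 3.2.1.1 lists the HADS comparison as secondary, and section 5.4.1 calls these analyses exploratory and not powered. The propranolol-versus-control comparison does not itself use HADS. Section 5.3.1 would adjust for psychosocial variables that are uneven between arms; if that uses baseline scores, both schedules supply them.

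Finally, the table does not match the text everywhere. Section 3.2.2.1b calls for a heart-rate and blood-pressure check after propranolol starts and before transplant, plus one just before transplant, yet that row has no Day -2 mark. So a mark lost in drafting or in conversion from PDF cannot be excluded. It would have to be two lost marks in the HADS row, and a look at the original page settles it.

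**Conclusion.** The contradiction is real: Table 4.7b provides a same-visit HADS at 1 of the 3 blood draws, and the section that cites it requires all 3. If sites follow the table, the Day -2 and Day 28 samples would have to borrow scores from 1 to 3 days later, after conditioning, and from 0 to 17 days away (nominally 7 days earlier). On the target of 30 complete gene datasets, that is 30 same-visit pairs in place of 90.

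The harm is limited to an exploratory secondary analysis and the Day +28 point of the HADS trajectory. The conclusion rests on two assumptions: that the table's empty cells are as printed, and, for any actual loss, that sites work from the table. The baseline discrepancy (Day -21 against Day -7) is a separate, smaller inconsistency. The point is worth correcting because the scores cannot be collected afterwards and the correction is nearly free.

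**What to change.** - In Table 4.7b, add HADS marks at Day -2 and Day 28.
- In section 4.6.2, make the baseline HADS day agree with the baseline blood-draw visit in section 4.4 and Table 4.7a.
- Reconcile the HADS row with the weekly rule in section 4.6.2. That rule follows the beta-blocker assessment, which under section 2.4 continues for one week after the drug stops, so it runs past Day 28 in the propranolol arm. State how long weekly HADS continues and whether it applies to controls.

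Optionally, ask for HADS at the visit where the sample is drawn. The protocol does not require the same day. With a Day 28 mark, HADS could fall on Days 25 to 31 (±3) and the sample on Days 21 to 35 (±7), so the two could still be 35 − 25 = 10 days apart.

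The cost is a table and text correction, plus a 14-item form at two visits that already include a blood draw and an adherence check.
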